3.2. EVALUATION OF ¹⁸F-AV-1451 PET IMAGES

Criteria for declaring an image invalid or not evaluable were specified in advance in the Image Review Charter. In this SAP, valid images will be considered as unevaluable only if at least 3 out of 5 independent readers declare the image unevaluable for the same reason(s).

¹⁸F-AV-1451 retention of PET images were interpreted by visual examination as either

- AD-: neocortical uptake not consistent with an AD pattern i.e., no increased neocortical activity in any region or increased activity is isolated to the mesial temporal, anterolateral temporal or frontal region(s);
- AD+: neocortical uptake consistent with an AD pattern i.e., increased neocortical tracer activity in the posterolateral temporal (PLT), parietal (including precuneus) or occipital region(s); or
- AD++: neocortical uptake consistent with an AD pattern and with likelihood of disease progression i.e., increased neocortical tracer activity is found in the parietal (including percuneus) region(s) regardless of uptake elsewhere (subset of AD+) or in the frontal region in addition to PLT, occipital or parietal region(s).

For the purpose of testing the primary analyses, a scan interpretation will be considered positive (hypothesized to correspond to a B3 NFT score for the first primary efficacy analysis and an NIA-AA score of high AD pathology for the second primary efficacy analysis) if the scan was interpreted as at least consistent with an AD pattern (AD+ or AD++).

Images were also assessed quantitatively (computerized measurement of Standard Uptake Value Ratios [SUVRs]) for exploratory analysis purposes.

The ¹⁸F-AV1451 PET imaging results will not be shared with the investigator sites or subjects and their families prior to the end of the study.

3.3. NEUROPATHOLOGICAL EVALUATION

All neuropathological measurements on brain tissue in this trial were evaluated in a standardized fashion in a qualified laboratory. In this SAP, subject autopsy specimens for which technical errors resulted in invalid or uninterpretable autopsy specimens (as determined by the pathology core laboratory in accordance with criteria set in the Technical Autopsy Manual and Neuropathology Analysis Plan) will be considered as being invalid and/or uninterpretable if the specimens were assessed as being ‘not evaluable’ for both hemispheres in the Braak Stage or NIA-AA autopsy diagnosis by the consensus panel, as appropriate for the primary efficacy endpoint #1 (refer to Section 15.1.1) and primary efficacy endpoint #2 (refer to Section 15.1.2).

Neuropathological assessment was derived from the NIA-AA guidelines (Hyman et al., 2012). Sections from brain regions recommended for pathological assessment of AD, as well as additional, pre-specified

Document:	\\quintiles.net\enterprise\Apps\sasdata\SASa\sas\AVID\18F-AV-1451\Biostatistics\Documentation\SAP\Avid_18F-AV-1451-A16_SAP_Final_v1.0_20180815.docx		
Author:	██████████	Version Number:	Final, v1.0
		Version Date:	15Aug2018
Template No:	CS_TP_BS016 – Revision 3	Reference:	CS_WI_BS005
Effective Date:	01May2012		

neocortical regions were sampled. Staining followed the procedures recommended in the NIA-AA practical approach guidelines. NFT extent was assessed using standard procedures and NFT score (B0-B3) was recorded (Hyman et al., 2012; Montine et al., 2012). The TS for the first primary efficacy analysis was constructed from NFT scores at autopsy as shown in Table 2.

Table 2 Autopsy NFT Score Truth Standard

Braak Stage	NFT Score ^A	Truth Standard
0 (no NFTs)	B0	
I-II	B1	Negative
III-IV	B2	
V-VI	B3	Positive

^A Adapted from Hyman et al., 2012.

Amyloid pathology was evaluated using Thal and CERAD rating systems. Distribution of amyloid (Thal plaque score A0-A3; Montine et al., 2012) was recorded. The frequency of neuritic amyloid plaques was evaluated semi-quantitatively (CERAD score: none, sparse, moderate or frequent). Potential alternative neuropathologies contributing to cognitive impairment were also considered, as recommended by Montine et al., 2012, and level of AD neuropathologic change was recorded as none, low, intermediate or high as per NIA-AA guidelines (Hyman et al., 2012; Montine et al., 2012). The TS for the second primary efficacy analysis was constructed from levels of AD neuropathological change as shown in Table 3.

Table 3 NIA-AA Autopsy Diagnosis Level of AD Neuropathological Change Truth Standard

Level of AD Neuropathological Change Present ^A	Truth Standard
None	
Low	Negative
Intermediate	
High	Positive

^A Adapted from Hyman et al., 2012.

3.4. BLINDING

A single Avid member performed periodic quality assurance (QA) by reviewing a listing of the PET image header data throughout the course of the study. These QA reviews served to ensure image quality control processes at the imaging core laboratory was adequately performed. Avid staff performing PET image data QA assessment was not aware of the clinical status for the subjects/images being reviewed and pathology data. After the independent visual reads was completed, PET scan images were transferred to Avid for SUVR analysis which was done blinded to visual read results and pathology data. Only designated Avid personnel responsible for image QC and SUVR analysis had access to the image data. All other Avid personnel are blinded to the Primary Efficacy Analysis Cohort ¹⁸F-AV-1451 PET images and visual read results as well as to the pathology data until database lock (DBL).

The independent visual readers and DMB were blinded to the subject clinical status and pathology data.

Document:	\\quintiles.net\enterprise\Apps\sasdata\SASa\sas\AVID\18F-AV-1451\Biostatistics\Documentation\SAP\Avid_18F-AV-1451-A16_SAP_Final_v1.0_20180815.docx		
Author:	XXXXXXXXXX	Version Number:	Final, v1.0
		Version Date:	15Aug2018
Template No:	CS_TP_BS016 – Revision 3	Reference:	CS_WI_BS005
Effective Date:	01May2012		

The pathological core laboratory was blinded to the subject clinical status, PET scan image(s), and visual read results.

IQVIA Biostatistical team (including statistical programmers) are blinded to the Primary Efficacy Analysis Cohort ¹⁸F-AV-1451 PET scan images, visual read results, and pathology data until DBL.

For additional details about blinding and unblinding, refer to the PET imaging read manual, pathological analysis manual, and Biostatistics Unblinding Plan, as appropriate.

Finally, an independent statistician who is not an employee of the Sponsor and who is not involved in the conduct and analysis of the study reviewed the pathology consensus data in an unblinded fashion after the third consensus panel meeting in order to determine if the sample size requirement/trial stopped criteria were met (i.e., at least 14 cases in each of the TS positive and negative categories have come to autopsy; refer to Section 7.1). The independent statistician was blinded to the PET scan images and visual read results.

3.5. CHANGES TO ANALYSIS FROM PROTOCOL

As per protocol Section 8.4, only ¹⁸F-AV-1451 PET images from subjects with valid autopsy data were to be interpreted by visual examination. However, all collected ¹⁸F-AV-1451 PET images of subjects who were still active in the study (i.e., who could potentially come to autopsy) at the time the visual reads were conducted, were interpreted by visual examination, regardless of the validity of the autopsy data.

During the study, it was identified that the imaging core laboratory (InVicro) included ~10% randomly selected scans for a second read by each imaging reader. This was a violation of the protocol. That is, rereads were not planned for this protocol because 1) the expected sample size for reads was small and 2) an intra-reader reliability has already been performed in a larger, target population-like sample population in study A05. Therefore, the second read data from this study will not be used for any analyses except for an intra-reader consistency evaluation (refer to Section 15.4).

4. PLANNED STATISTICAL ANALYSES

No interim analysis (IA) or analysis for a Data Safety Monitoring Board (DSMB) committee were performed. That is, the only statistical analysis that will be performed for this study is the final analysis. This analysis will be performed by IQVIA Biostatistics following Sponsor authorization of this SAP, DBL, and study unblinding. Considering that the definition of each analysis set defined in this SAP (refer to Section 5) does not include any subjective criterion, Sponsor approval of this SAP will stand for the Sponsor approval of the inclusion/exclusion of each subject in/from each analysis set.

Document:	\\quintiles.net\enterprise\Apps\sasdata\SASa\sas\AVID\18F-AV-1451\Biostatistics\Documentation\SAP\Avid_18F-AV-1451-A16_SAP_Final_v1.0_20180815.docx		
Author:	██████████	Version Number:	Final, v1.0
		Version Date:	15Aug2018
Template No:	CS_TP_BS016 – Revision 3	Reference:	CS_WI_BS005
Effective Date:	01May2012		

5. ANALYSIS SETS

5.1. ALL SUBJECTS ENROLLED SET

The all subjects enrolled analysis set (ENR) will contain all subjects who provided informed consent and received at least one ¹⁸F-AV-1451 injection. Subjects who provided informed consent, completed screening evaluation but did not receive any ¹⁸F AV-1451 injection will be treated as screen failures and will not be analyzed.

This analysis set will be used to summarize subjects' disposition, major protocol deviations, and analysis sets data (refer to Section 9). Summaries will be presented overall and by most recent neurological disease diagnosis i.e., normal, mild cognitive impairment, and dementia.

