7.7.2. Adverse Event Definitions

Adverse Events

For reporting purposes, Avid will distinguish among pre-existing conditions, treatment emergent adverse events and trial-emergent adverse events. Pre-existing conditions (i.e., undesirable experiences, signs or symptoms that begin prior to the Screening Visit) will be recorded on the medical history and/or physical exam eCRF pages. Signs and symptoms that are believed to be due to the pre-existing condition (started prior to dose of investigational product) do not have to be recorded in the AEs section of the eCRF, unless there is an increase in frequency or severity. Additionally, signs or symptoms or changes in pre-existing conditions that occur outside the trial-defined adverse event reporting will be recorded in medical history.

An adverse event is any untoward medical occurrence associated with the use of a drug in humans, whether or not considered drug related. For the purposes of this study, untoward medical occurrences will be considered associated with the use of ¹⁸F-AV-1451, and thus be reported as treatment-emergent adverse events, if they occur within 48 hours after ¹⁸F-AV-1451 administration.

In the context of this study, adverse experiences including hospitalizations, medical complications and death are expected, since terminal illness is a requirement for entry into the study. Thus, if the investigator becomes aware of such events that occur after administration of the drug but outside the 48 hour reporting window, these will only be reported as adverse events if the investigator believes they are attributable to the investigational product or protocol procedure.

In order to capture possible adverse effects of trial participation, any untoward medical occurrences occurring after the informed consent until the administration of ¹⁸F-AV-1451 will be recorded in the CRF for reporting as trial-emergent adverse events. If the subject consents to a second ¹⁸F-AV-1451 PET scan, trial-emergent adverse events will be collected in a similar period, from either date of additional consent (if applicable) or the date the dose request for the second scan is submitted to Avid, up to the second administration of ¹⁸F-AV-1451.

Serious Adverse Event (SAE)

An SAE is an AE that results in one of the following outcomes or constitutes one of the following events:

- Death;

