7.7.4. Reporting of Serious Adverse Events

Study site personnel must alert Eli Lilly or its designee of any SAE within 24 hours of their awareness of the event via a sponsor-approved method. Alerts issued via telephone are to be immediately followed with official notification on study-specific SAE forms.

Serious adverse events occurring after a subject receives a dose of investigational product will be collected until 48 hours after the dosing of the investigational product, regardless of the investigator's opinion of causation. Therefore, SAEs that occur later than 48 hours after the dosing of the investigational product are not required to be reported unless the investigator feels the events were related to either investigational product or a protocol procedure.

If a subject experiences an SAE after signing informed consent(s), but prior to receiving investigational product, the event will be reported on the eCRF and to Eli Lilly or its designee. Previously planned (prior to signing the ICF) surgeries should not be reported

as SAEs unless the underlying medical condition has worsened during the course of the study.

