8.3. Safety Analysis

Safety vital signs measurements will be summarized by subject and by evaluation time point. Change from baseline (pre-dose time point) values will be determined and summarized.

Adverse events including injection site reactions will be summarized in terms of number and percentage of subjects experiencing an AE. The summary will be further broken down by system organ class (SOC) and preferred term using Medical Dictionary for Regulatory Activities (MedDRA) terms. Adverse events will also be presented by severity, relationship to treatment and seriousness. All subjects who experience SAEs or who discontinue due to AEs will be summarized.

Discontinuation

All subjects who discontinued participation prior to completing the study will be listed and their discontinuation reasons will be tabulated.

Vital Signs

Changes in vital signs from baseline will be summarized.

8.4. ¹⁸F-AV-1451 Image Analysis

¹⁸F-AV-1451 retention on PET images from subjects with valid autopsy data will be interpreted by visual examination as either

- Neocortical Uptake Not Consistent with an AD Pattern (AD-: no increased neocortical activity in any region or increased activity is isolated to the mesial temporal, anterolateral temporal or frontal region(s);
- Neocortical Uptake Consistent with an AD Pattern (AD+: increased neocortical tracer activity in the posterolateral temporal (PLT), parietal (including precuneus), or occipital region(s)); or
- Neocortical Uptake Consistent with an AD Pattern and with Likelihood of Disease Progression (AD++, which is a subset of AD+ (Neocortical uptake consistent with an AD pattern) where increased tracer activity is found in the parietal (including precuneus) region(s) regardless of uptake elsewhere, or in the frontal region in addition to PLT, occipital, or parietal region(s)).

For the purpose of testing the primary analyses, a scan interpretation will be considered positive (hypothesized to correspond to a B3 neuropathology score in Primary Analysis 1 and an NIA-AA score of high AD pathology in Primary Analysis 2) if the scan is interpreted as at least consistent with an AD pattern (AD+ or AD++). Details of the visual PET image review methods will be provided in the Blinded Read Manual.

Images will also be assessed quantitatively (semi-automated computerized measurement of SUVRs) for exploratory analysis purposes. Details of the analysis methods will be provided in the Quantitative Methodology Document.

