5.2. SAFETY ANALYSIS SET

The safety analysis set (SAF) will be the same as ENR i.e., include all subjects who provided informed consent and received at least one ¹⁸F-AV-1451 injection.

This analysis set will be used to summarize demographic and other baseline characteristics (refer to Section 10), medical/surgical history, concurrent medical conditions/diseases, family neurological disease history, and subjects neurological disease history (refer to Section 11), concomitant medications (refer to Section 12), cognition assessments at screening (refer to Section 13), exposure to ¹⁸F-AV-1451 (refer to Section 14), and all safety data (refer to Section 16). Summaries will be presented overall and by most recent neurological disease diagnosis.

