9. DISPOSITION AND WITHDRAWALS

All subjects who provide informed consent, meet all inclusion/exclusion criteria and have received at least one ¹⁸F-AV-1451 injection will be accounted for in this study.

The numbers and percentages of subjects enrolled, who received at least one ¹⁸F-AV-1451 injection, completed the study, and discontinued early from the study as well as the reason for early discontinuation will be summarized based on the ENR overall and by most recent neurological disease diagnosis. For the analysis purpose, study completion will be defined as subjects who died within nine months of their most recent ¹⁸F-AV-1451 PET scan and had an autopsy performed.

Document:	\\quintiles.net\enterprise\Apps\sasdata\SASa\sas\AVID\18F-AV-1451\Biostatistics\Documentation\SAP\Avid_18F-AV-1451-A16_SAP_Final_v1.0_20180815.docx		
Author:	XXXXXXXXXX	Version Number:	Final, v1.0
		Version Date:	15Aug2018
		Reference:	CS_WI_BS005

Template No: CS_TP_BS016 – Revision 3
Effective Date: 01May2012

Copyright © 2012 Quintiles Transnational Corp. All rights reserved.

The contents of this document are confidential and proprietary to Quintiles Transnational Corp. Unauthorized use, disclosure or reproduction is strictly prohibited.

The numbers and percentages of subjects with any critical and/or major protocol deviation (as defined by the clinical team during the course of the study and finalized before database lock) will be summarized based on the ENR overall and by most recent neurological disease diagnosis. The number and percentages of subjects with at least one protocol deviation in each type of protocol deviation will be summarized similarly by severity (critical/major), where type of protocol deviations are:

- Administrative criteria
- Compliance with investigational product
- Concomitant medication criteria
- Eligibility and entry criteria
- Informed consent
- Laboratory assessment criteria
- Other criteria
- Serious adverse event criteria
- Source document criteria
- Study procedures criteria
- Visit schedule criteria

Summaries will be presented in decreasing order of type of protocol deviation within each severity (critical/major). Minor protocol deviations which will be presented in subjects data listing only.

The numbers and percentages of subjects included in/excluded from each analysis set and reasons for exclusion from each analysis set will be summarized based on the ENR overall and by most recent neurological disease diagnosis.

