16.1.4. SERIOUS ADVERSE EVENTS

Serious adverse events (SAEs) are those events recorded as “Serious” on the AEs page of the eCRF. Incidence of SAEs will be presented by SOC and PT. A listing containing all SAEs will also be prepared.

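### Consented subjects who are never injected enter no summary described in the SAP, adverse events between consent and injection have no planned summary for anyone, and the SAE and fatal-event tables can mix pre- and post-injection events

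*SAP*

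**What the plan says.** **Analysis sets.** SAP 5.1 states: "The all subjects enrolled analysis set (ENR) will contain all subjects who provided informed consent and received at least one" injection of the tracer. For subjects who consent and complete screening but are not injected, the rule ends "injection will be treated as screen failures and will not be analyzed". SAP 5.2 adds: "The safety analysis set (SAF) will be the same as ENR". Subjects who consent but do not finish screening are not named, but they too are outside both sets because they have no injection.

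**Disposition.** SAP Section 9 reports "The numbers and percentages of subjects enrolled, who received at least one" injection, on ENR. The same section summarises causes of death on SAF.

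**Adverse events in the protocol.** Protocol 7.7.2 separates pre-existing conditions, treatment-emergent events and trial-emergent events for reporting. It defines the last group thus: "In order to capture possible adverse effects of trial participation, any untoward medical occurrences occurring after the informed consent until the administration of" the tracer. These are to be recorded on the case report form. The same rule applies before a second injection. Protocol 7.7.4 states: "If a subject experiences an SAE after signing informed consent(s), but prior to receiving investigational product, the event will be reported on the eCRF", and it is also reported to the safety recipient. Protocol 8.3 says that all subjects with SAEs will be summarised, and separately: "All subjects who discontinued participation prior to completing the study will be listed and their discontinuation reasons will be tabulated".

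**Adverse events in the SAP.** Section 16 bases safety outputs on SAF. Section 16.1 defines treatment-emergent events as running from an injection to 48 hours after it, and defines no trial-emergent category. Section 16.1.4 says "Incidence of SAEs will be presented by SOC and PT", with no time limit, and 16.1.3 (fatal events) is worded the same way. Section 16.1.5 (events leading to discontinuation) is limited to treatment-emergent events. Section 16.1 promises listings of all AEs, and Appendix 1 promises listings of all eCRF data.

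**The concern.** The protocol collects pre-injection events in order to see harm from taking part. In this population that is a real possibility. Subjects have a projected life expectancy of six months or less (protocol 5.3.1), screening may precede the scan by up to about 45 days (protocol 7.1.1), and a physician must judge tolerability before dosing (protocol 7.1.2). Deterioration, an SAE or death in that interval is a foreseeable reason for not being injected. A summary limited to injected subjects then leaves people out because of the events it was meant to count.

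Two outputs are affected. The disposition table cannot show how many consented subjects never reached the scan, or why. The SAE and fatal-event tables have no defined period of risk, so a reader cannot take them as safety after the tracer or as safety during participation.

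**Working it through.** The documents give no sample size, power or error rate that bears on this, so there is no planned figure to reproduce. The check is set logic, a comparison of sections, and one illustrative range.

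**Step 1: percentage injected.** Every ENR member has been injected (SAP 5.1), and Section 9 uses ENR as the denominator. Injected / ENR = ENR / ENR = 100%, whatever the data. The row carries no information.

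**Step 2: where each kind of event goes under the SAP text.**

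| Event | Subject who is injected | Subject never injected |
|---|---|---|
| Non-serious, non-fatal AE between consent and injection | No summary; listing only | No summary; listing unclear |
| SAE or fatal AE with onset between consent and injection | Can enter the tables in 16.1.3 and 16.1.4 | No summary; listing unclear |
| AE from injection to 48 hours | Treatment-emergent tables | Not applicable |

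The first row shows that the missing trial-emergent summary does not come from the ENR definition alone. The general AE tables are confined to treatment-emergent events, so dosed subjects have no such summary either. Widening ENR without adding a table would leave the gap open. The second row shows the asymmetry: the same kind of event can be counted or omitted according to whether the subject was later dosed.

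The listing cells are unclear for undosed subjects because the promises to list all AEs and all eCRF data sit beside a rule that these subjects are not analysed and a section that bases safety outputs on SAF. The SAP does not say which prevails.

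**Step 3: protocol against SAP.** Protocol 8.3 has all subjects with SAEs summarised, and 7.7.4 requires pre-dose SAEs to be recorded. SAP 16 restricts the SAE summary to SAF, so a never-injected subject with an SAE is recorded but not summarised. SAP 3.5, which lists changes from the protocol, mentions neither this restriction nor the absence of a trial-emergent category.

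**Step 4: illustrative size.** Inputs: 200 injected (the approximate planned number enrolled and imaged, protocol synopsis and 5.1) and a share d of consented subjects never injected. The documents give no value for d, so 2% to 20% is an assumption.

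Consented N = 200 / (1 − d), rounded up; uninjected = N − 200; percentage injected of those consented = 100 × 200 / N.

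| d (assumed) | 200 / (1 − d) | Consented N | Never injected | Injected, % of consented |
|---|---|---|---|---|
| 2% | 204.1 | 205 | 5 | 97.6 |
| 5% | 210.5 | 211 | 11 | 94.8 |
| 10% | 222.2 | 223 | 23 | 89.7 |
| 15% | 235.3 | 236 | 36 | 84.7 |
| 20% | 250.0 | 250 | 50 | 80.0 |

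In every row the SAP's own denominator would report 100%.

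**The case against.** The case for leaving the SAP alone has several parts.

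- **The data are not lost.** A reader might infer that they are. The documents do not support that: pre-dose events stay on the eCRF, pre-dose SAEs are still reported, and the SAP promises listings of all AEs and all eCRF data. This stands. What remains is that a listing is not a summary, and that its coverage of undosed subjects is unstated.
- **A listing might satisfy protocol 7.7.2.** That section prescribes no format, and 8.3 does not promise a separate trial-emergent table. This also stands, so it would go too far to say that the protocol's purpose cannot be met. But 8.3 does say that subjects with SAEs are summarised, and a listing falls short of that.
- **An injected-only safety set is conventional.** Agreed, and nothing here asks to change it. The protocol also speaks of subjects being enrolled and imaged, so equating enrolment with injection is defensible. The redundant row is then minor in itself.
- **Protocol 8.3 on discontinuations.** A reader might infer that the SAP contradicts the rule that all who discontinue are tabulated. The protocol does not say that a screen failure counts as a discontinuation, so that contradiction is not established.
- **Unseen documents.** The SAP follows protocol amendment 3, while the protocol available is amendment 2. Table formats and content are left to shells that are not available. Screen-failure counts or a split by onset could be there, so the finding is confined to the SAP text.
- **The number may be near zero.** Some screening can take place on the imaging day with sponsor approval (protocol 7.1.1), so the interval can be short. The range above is arithmetic on an assumed rate.

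**Conclusion.** The point holds for the SAP text. Consented subjects who are never injected are in no summary it describes, and the percentage injected on ENR is 100% by construction. Trial-emergent events have no planned summary for dosed or undosed subjects, mainly because the SAP has no such category. The SAE and fatal-event tables have an undefined time window and treat the same pre-injection event differently according to later dosing. For SAEs this falls short of protocol 8.3, and SAP 3.5 does not declare it.

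The size is unknown: about 5 to 50 subjects per 200 injected under the assumed 2% to 20%. The definitional defects do not depend on that rate. The effect is limited to disposition and pre-injection safety reporting. Never-injected subjects have no scan, so the efficacy sets and the criterion of 14 cases per truth-standard group are unchanged. The treatment-emergent tables, which are the main description of tracer safety, are also unchanged.

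**What to change.** - **SAP 5.1 and 5.2:** keep SAF as injected subjects, and add or define a set of all consented subjects for the outputs below.
- **SAP 9:** report the numbers consented, injected and not injected, with reasons, on an all-consented denominator. This replaces the row that is always 100%.
- **SAP 16.1:** define trial-emergent events as in protocol 7.7.2, and add a summary of trial-emergent AEs and SAEs for all consented subjects. State how events in the protocol's collection period before a second injection are assigned.
- **SAP 16.1.3 and 16.1.4:** split the fatal-event and SAE tables into pre-injection and post-injection events.
- **SAP 16.1 and Appendix 1:** state which set the AE listings use and whether it includes never-injected subjects.
- **SAP 3.5:** declare any departure from protocol 7.7.2 or 8.3 that is kept.

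The cost is SAP wording, one or two extra tables and a column split in two others. The protocol already requires the events on the eCRF, so no new data are needed.
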